Target Population: Children (aged 4-15) in mainstream school settings with a diagnosis of ASD according to ICD-10 research diagnostic criteria (WHO, 1993), ADI-R (Lord et al, 1994) and ADOS (Lord et al, 2000), who exhibit challenging behaviour in the school setting. This will be assessed using instruments informed by the systematic review (examples include the Strengths and Difficulties Questionnaire (SDQ) and the Developmental Behaviour Checklist (DBC)). We will also set a clear goal with the child, family and teacher and rate it using Likert scales before and after the study. Schools will be approached through an existing network of clinical and educational practitioners and researchers led by co applicant [name].

Intervention: A manualised toolkit of appropriate Social Stories for use with school aged children exhibiting challenging behaviour within the mainstream school setting. The toolkit and exact methodology of the feasibility study will be determined in earlier phases of the study. The comparator treatment will be an attention control.

Both arms will receive treatment as usual, for example, behavioural approaches, parenting support, systemic approaches and social skills training.

Outcomes: Primary Outcomes: utility and acceptability to parents/teachers/children of using the manualised Social Stories intervention in a mainstream school setting, as assessed by qualitative interviews and questionnaires. Secondary Outcomes: Acceptability of the research methods (e.g. randomisation procedure) to parents /carers /teachers/ children. Standard deviations of the measures used (e.g. SDQ, DBC, Likert Scales) in the two groups (Social Stories and attention control) to inform power calculation.

Economic Evaluation: The economic evaluation will take the form of within-trial costeffectiveness analysis that will determine the incremental cost per unit of effectiveness measure for Social Stories compared with an attention control in children with autism.

Sample Size: 10 parents, 5 children/young people, 5 teachers and 5 non research clinicians will be involved in the qualitative interview phase. The manualised intervention will be delivered to 25 children (and 25 children in the control group) in our feasibility study, where we will demonstrate recruitment, attrition and follow up rates, with preliminary estimates of effect size to inform sample size calculations for a full trial.

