3.3.3 Recruitment

Interested families will be invited to meet a researcher for further information if their child has a diagnosed ASD and behavioural problems in a mainstream school. We will recruit 50 children attending mainstream schools, with autism spectrum disorders (Autism, Asperger syndrome and Atypical autism), using ICD-10 research diagnostic criteria [RDC] (46), supported by ADI-R (47) and/or ADOS (48). Other developmental disorders will not be included.

Schools will be approached to take part in the study through an existing network of clinical and educational practitioners and researchers. Co-applicant [name] has previously facilitated many research studies across the full range of schools as part of his role within the Local Authority. There are 72 primary schools in the York Local Authority and 10 secondary schools. Two of these secondary schools are designated as ASD supportive schools, although all the other schools have some young people with ASD within them. We have already had preliminary discussions with a number of secondary and primary schools that are supportive of this bid and we are confident that we can recruit 30 children within primary schools and 20 young people within secondary schools without difficulty. We anticipate that this will be in 4 secondary schools and 10 primary schools, although we will test the feasibility of this and be adaptable to recruit more or less by rolling out school involvement and leaving enough time in the study for flexibility. We will stratify school randomization to take into account numbers of ASD children, levels of ASD support, socio economic indices and Ofsted value added scores. We will ask the local multi agency autism strategy group to compare the two groups of schools generated for equivalence. Any concerns will be fed back to the steering group and the matching process will be considered as part of the feasibility work.

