3.3.4 Randomization

We will adopt a cluster randomization approach. This is to minimize the likelihood of participants in the different intervention groups being affected by changes in teacher or school behaviour. It also recognizes that social story expertise within a school is likely to be enhanced by sharing of skills and networking of ideas, and this design therefore more accurately reflects what would happen if social stories were used within a school in practice. We will use the qualitative interviewing within the feasibility design to explore this further, as described below.

To reduce detection bias we will first recruit the mainstream schools to be involved in the study. Then subsequently we will consent children and their families within these selected schools for involvement in the study. Only then will we randomize the schools into schools where the intervention takes place and those where it does not but where we are monitoring outcomes in the same way as in the intervention school. Participants will be randomised at whole school level, thus all children with ASD within any given school will be randomised to the same arm of the trial. This will minimize contamination as the likelihood of participants in the different intervention groups being affected by changes in teacher or school behaviour will be reduced. In order to limit detection bias, participants will be receive the Social Story intervention. The control school children will receive an equivalent amount of time reading a story of similar length and linguistic complexity a range of which will be chosen by the expert panel as an attention control. In both schools children will receive all other treatment or support as usual and we will monitor carefully what this is.

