3.3.10 Proposed sample size

We will use the information gathered in the pre-clinical theory stage of the study to determine sample sizes needed for the feasibility study / phase 2 of the study. The sample

size will be determined in order to be adequate to estimate the critical parameters for a full RCT. We will be estimating recruitment rate. With 50 participants in total we will be able to estimate the recruitment rate to within 10% based on 85% recruitment, using a 95% confidence interval (Dixon & Massey, 1983). We will demonstrate recruitment and follow up rates, with preliminary estimates of effect size to inform sample size calculations in a fully powered RCT.

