- 2. Strengths and Difficulties Questionnaire (SDQ; (50)), which includes conduct, hyperactivity and prosocial subscales (parent, child, teacher)
- 3. Likert Scales for target behaviours designed and agreed by the focus groups/ expert panel (parent, child, teacher, and clinician). In this way we will develop a goal based outcomes scale and test its usefulness against the other instruments as part of our feasibility study.
- 4. Generalisability will be assessed using questionnaires designed for each individual child that ask about the frequency of challenging behaviours for both the Social Story target behaviour and for other associated or related behaviours (e.g. if more positive behaviours in the class result in reduced destruction in the class are there also reductions seen in other settings, such as the dining hall, home etc). These will be parent and teacher based questionnaires used before and after the intervention.

- 5. General Health Questionnaire (parents)
- 6. Intervention Rating Profile (51), which has been widely used to assess parents views of interventions used with their children. A separate questionnaire will be developed to be administered by parents to their child to assess the views and experiences of the child of using Social Stories.

Descriptive statistics will be calculated for recruitment rates, follow-up rates and attrition. Descriptive statistics and 95% confidence intervals will be calculated for the outcome measures. We will use the data to develop estimates for a fully powered RCT that will include estimates of change in outcome measures over time taking into account attrition and follow up rates.

Although the feasibility study is not powered to detect differences in outcome measures we will undertake inferential statistics (Chi-squared tests for categorical data, t- tests for continuous data, and Mann-Whitney tests for ordinal data). All analyses will be undertaken on SPSS version 17.

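### Schools are randomised, but section 3.3.14 fixes t, chi-squared and Mann-Whitney tests with no allowance for school; if outcomes cluster by school, the p-values and between-arm intervals are too optimistic

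*Protocol*

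**What the plan says.** Section 3.3.4 is explicit about the unit of randomisation: "We will adopt a cluster randomization approach", and "Participants will be randomised at whole school level, thus all children with ASD within any given school will be randomised to the same arm". Section 3.3.3 gives the expected layout: "We anticipate that this will be in 4 secondary schools and 10 primary schools", and the team is confident that "we can recruit 30 children within primary schools and 20 young people within secondary schools without difficulty". The Summary (Sample Size) splits the 50 children 25 and 25.

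Section 3.3.14 then fixes the analysis. It promises descriptive statistics and 95% confidence intervals for the outcome measures. After conceding that the study is not powered for outcome differences, it states that "we will undertake inferential statistics (Chi-squared tests for categorical data, t- tests for continuous data, and Mann-Whitney tests for ordinal data". It mentions no school-level summary, random effect, robust variance or design effect, and neither does any other section. Clustering appears only as a design rationale (3.3.4), in the stratification of schools (3.3.3) and as a topic for the qualitative interviews (3.3.13).

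For the full trial, the Summary names "Standard deviations of the measures used (e.g. SDQ, DBC, Likert Scales) in the two groups" as input to the power calculation. Section 3.3.10 adds recruitment and follow-up rates and effect size, and section 3.3.14 adds change over time, attrition and follow-up. No section names an ICC or the variation in cluster size.

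**The concern.** In their standard form, all three tests assume independent observations. When whole schools are allocated, the between-arm comparison carries between-school variation as well as between-child variation, and a test that counts children leaves the first part out of its standard error. The protocol itself gives reason to expect such variation. Section 3.3.4 chooses clusters because teacher and school behaviour may affect participants and because expertise is shared within a school. Section 3.3.13 looks for systemic as well as individual effects.

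Two things are at stake. The first is the reported p-values and between-arm intervals, which would look more precise than the design supports. The second is what the study hands on: a feasibility study meant to estimate the critical parameters for a full trial does not name the one parameter that a cluster-randomised successor needs beyond the standard deviation.

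**Working it through.** **The plan's own figure.** Section 3.3.10 says that 50 participants estimate an 85% recruitment rate to within 10%. 1.96 × √(0.85 × 0.15 / 50) = 0.099, so the figure reproduces. It is a simple binomial calculation that counts 50 independent children. It is not in dispute here and gives no allowance for school to carry forward. The plan gives no figure for the outcome comparison.

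**Inputs.** From section 3.3.3: 10 primary schools with 30 children (3 each) and 4 secondary schools with 20 children (5 each), so 14 schools. From the Summary: 25 children per arm. The ICC is not given; 0.01 to 0.20 is assumed.

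**Design effect.** The size-weighted mean cluster is (10 × 3² + 4 × 5²) / 50 = 190 / 50 = 3.8, so DE = 1 + (3.8 − 1) × ICC = 1 + 2.8 × ICC. Effective sample size = 50 / DE.

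**Real error of the nominal 5% t-test.** A normal approximation is 2 × [1 − Φ(1.96 / √DE)]. Null trials were also simulated with 5 primary and 2 secondary schools per arm.

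**Interval width.** A between-arm interval that respects the design has √DE times the standard error and uses t on 14 − 2 = 12 df instead of 50 − 2 = 48 df. The ratio is √DE × 2.179 / 2.011 = √DE × 1.084.

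| Assumed ICC | DE | Effective N | Error, approximation | Error, simulated t-test | Correct / unadjusted width |
|---|---|---|---|---|---|
| 0.01 | 1.03 | 48.6 | 5.3% | about 5.5% | 1.10 |
| 0.05 | 1.14 | 43.9 | 6.6% | about 6.6% | 1.16 |
| 0.10 | 1.28 | 39.1 | 8.3% | about 8.4% | 1.23 |
| 0.20 | 1.56 | 32.1 | 11.7% | about 11.7% | 1.35 |

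The Mann-Whitney test behaves much the same (5.2%, 6.5%, 8.1%, 11.3%). A t-test on school means stays at about 5% throughout. The factor 1.084 applies even at ICC 0: it is the price of estimating between-school variance from 14 schools. Only the rest of the widening comes from correlation.

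**What 14 schools can say about the ICC.** With mean cluster size m = 50 / 14 = 3.57 and k = 14, the approximate SE is √{2(1 − ICC)²[1 + (m − 1)ICC]² / [m(m − 1)(k − 1)]}. At ICC 0.10 this is √{2 × 0.81 × 1.257² / (3.57 × 2.57 × 13)} = 0.146, so the 95% interval runs from about −0.19 to 0.39. At 0.05 and 0.20 the SE is 0.139 and 0.157.

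**Consequence for a clustered full trial (illustration only).** Assume a standardised difference of 0.5, 80% power, two-sided 5%, and the same mean cluster size. Without clustering, 63 per arm are needed. Multiplying by 1 + 2.57 × ICC gives 72, 80 and 96 per arm at ICC 0.05, 0.10 and 0.20.

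**The case against.** The strongest reply is that these tests matter little. The protocol says the study is not powered for outcome differences, its primary outcomes are utility and acceptability, no main outcome measure has been chosen, and no progression or stopping rule depends on a p-value. This stands, and it limits how serious the point is. It does not make the tests right, and the intervals remain a stated output.

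The size is conditional. At ICC 0.01 the error rate barely moves. The stratification in 3.3.3 (ASD numbers, ASD support, socio-economic indices, Ofsted scores) could lower the true error where those factors explain school differences. Fourteen schools is itself an expectation. Many measures are rated by parents or children, so one ICC need not serve all of them. All of this stands.

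The protocol does not use the term child-level, nor say whether its 95% intervals are per arm or between arms. Child-level is nevertheless the natural reading of these tests with 25 against 25 children, and the criticism of the intervals is confined to between-arm ones. An unseen analysis plan could add detail, but the protocol itself fixes the tests.

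A reader might go further on three points, which the document does not support:

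- That one teacher rates several of the children in a school: section 3.3.14 says only that teachers complete questionnaires.
- That the full trial will be cluster randomised: sections 2.1, 3.3.17 and 5.0 do not say so. It is plausible from the reasons in 3.3.4.
- That the full trial will be sized on standard deviations alone, so that no ICC can reach it: the parameter list in 3.3.14 is open-ended and 3.3.10 speaks of critical parameters generally. An ICC is unplanned, not ruled out.

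**Conclusion.** The mismatch between the design and the named tests is real and lies in the protocol text. Followed as written, the analysis gives standard errors that are too small whenever the school ICC is above zero. With the planned layout, the real error of a nominal 5% t-test is about 5.5% to 11.7% over assumed ICCs of 0.01 to 0.20, and correct between-arm intervals are about 10% to 35% wider, including the degrees-of-freedom factor. These figures rest on the assumed ICCs, on 14 schools of 3 or 5 children, and on stratification removing no between-school variance. The effect is moderate because the clusters are small.

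The planning gap is conditional too: the ICC and cluster-size variation are needed if the full trial also randomises schools. The point should be corrected, but it does not threaten the study's main objectives.

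**What to change.** In section 3.3.14, replace the sentence naming the unadjusted tests. Any of three routes resolves it:

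- a mixed model with a random school effect and small-sample degrees of freedom, with cluster-adjusted methods for categorical and ordinal outcomes;
- an analysis of school-level summaries;
- no hypothesis tests, reporting cluster-adjusted estimates with 95% confidence intervals, which suits a study declared not powered for outcomes.

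Compute every between-arm interval the same way.

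Add to the reported parameters, for each candidate outcome, the ICC with its confidence interval and the variation in cluster size. State that about 14 schools give an imprecise ICC (SE about 0.15), so the full trial should plan over a range and read it alongside external values.

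The cost is a wording change, a little more analysis and somewhat wider intervals. It needs no new data and no change to recruitment or conduct.

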3.3.12 Follow-up

Follow-up will be for a minimum of six months post-randomisation. Where a participant has been lost to follow-up their data will be included in the main analysis up to where they have been lost to follow-up. Where a participant is lost to follow-up, efforts will be made to contact the participant.

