3.3.14 Quantitative Collection and Analysis

The following questionnaires will be completed at three times; before, six weeks into the trial and six months after the trial. Teachers, parents and children will complete the Strengths and Difficulties Questionnaires, Developmental Behaviour Checklist, and the generalisability questionnaire about the children. Parents will complete the General Health Questionnaire about themselves. The target behaviour will be agreed at the beginning of treatment and the outcome questionnaire completed at 6 weeks and six months into the trial.

This will enable us to examine the change in behaviour scores over the course of the intervention and monitor whether the skills learnt are maintained over a longer period.

Change in parental stress will be measured using the General Health Questionnaire at the beginning, midpoint and end of the trial. We will also assess acceptability to parents and teachers using a 12 item Intervention Rating Profile at the end of the study. We will examine the effects of diagnosis and age of the participants when carrying out the analysis. Qualitative interviewing will take place to obtain feedback about acceptability and utility to parents and carers.

We are carrying out a feasibility study to assess parameters such as:

- willingness of children and young people and their parents to participate
- issues around consent and assent in children and young people with ASD
- acceptability of the intervention with children, young people and families
- acceptability of not receiving the intervention
- qualitative aspects around the process of delivery of the intervention including who delivers it and how it is formulated, when and how it is delivered and for how long
- acceptability of training for teachers and other staff, and the feasibility of arranging an delivering training in a busy school environment (e.g. release for training)
- follow up and response rates
- attrition and non compliance rates
- characteristics and utility of the outcome measures

At this point we have not chosen a main outcome measure as it is one of the purposes of the feasibility study to explore which outcome measures are most likely to be useful, which may include:

- 1. Developmental Behaviour Checklist (DBC; (49)), which includes ASD subscales and a disruptive subscale (parent and teacher)

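### The outcome tests carry no baseline term and do not say whether final or change scores are compared; a baseline-adjusted model that allows for school would be more precise at no extra data cost

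*Protocol*

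**What the plan says.** Section 3.3.14 states that, although the study is not powered for outcome differences, the arms will be compared by inferential tests: chi-squared for categorical outcomes, "t- tests for continuous data, and Mann-Whitney tests for ordinal data". No covariate and no repeated-measures model is named for these comparisons. The same section says that the effects of age and diagnosis will be examined, without a method and without mention of the baseline score.

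Baseline scores will exist. The SDQ, DBC, generalisability questionnaire and GHQ are "completed at three times; before, six weeks into the trial and six months after the trial". The section links this schedule to change: "This will enable us to examine the change in behaviour scores over the course of the intervention". It also plans "estimates of change in outcome measures over time taking into account attrition and follow up rates" for the full trial.

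Section 3.3.12 says of participants lost to follow-up that "their data will be included in the main analysis up to where they have been lost to follow-up".

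Sections 3.3.3 and 3.3.4 randomise whole schools, an anticipated 10 primary and 4 secondary. They stratify on number of ASD children, ASD support, socio-economic indices and Ofsted scores. No child-level behaviour score is balanced.

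**The concern.** The protocol collects the variable most likely to explain variation in the follow-up score, then names tests with no place for it as a covariate. With 50 children in about 14 schools, and ages from 4 to 15, the arms may well differ at baseline by chance.

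The choice of score is also left open. A test of final scores and a test of change scores have different variances and react to baseline imbalance in opposite directions. Choosing between them after seeing the data would be a free choice of result.

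The stake is the full trial. The Summary makes the SDs of the measures a secondary outcome so that they can inform a power calculation, and section 3.3.10 wants preliminary effect sizes for the same purpose. Two-sample tests yield neither the baseline-follow-up correlation nor the residual SD on which an efficient full trial would be sized.

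**Working it through.** **The plan's own figure.** The only precision statement (section 3.3.10) concerns recruitment: 1.96 × √(0.85 × 0.15 / 50) = 0.099, which agrees with the stated 10%. It does not bear on the outcome tests.

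**Inputs.** From the protocol: 25 children per arm (Summary); 30 primary and 20 secondary pupils in 10 and 4 schools (section 3.3.3). Not given, hence assumed as ranges: baseline-outcome correlation ρ, intraclass correlation (ICC) and loss to follow-up. Follow-up and baseline SDs are taken as equal, and results are in SD units.

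**Precision, with clustering ignored in all three analyses.** 95% half-widths:
- final-score t-test: t(48) × √(2/25) = 2.011 × 0.283
- change-score t-test: the same × √(2(1 − ρ))
- baseline-adjusted (ANCOVA): t(47) × √(1 − ρ²) × √(2/25) × √(1 + 1/46), with t(47) = 2.012

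| ρ | Final | Change | Adjusted | Final ÷ adjusted | Change ÷ adjusted |
|---|---|---|---|---|---|
| 0.3 | 0.569 | 0.673 | 0.549 | 1.04 | 1.23 |
| 0.5 | 0.569 | 0.569 | 0.498 | 1.14 | 1.14 |
| 0.7 | 0.569 | 0.441 | 0.411 | 1.38 | 1.07 |

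The adjusted residual variance is 1 − ρ² of the raw variance: 0.91, 0.75 and 0.51. Before any allowance for clustering, a sample size based on the raw SD would differ from one based on the adjusted SD by the same factor. These figures are for the t-test; no separate figure was derived for the Mann-Whitney test.

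**Chance imbalance.** The SD of the baseline difference between arms is √(2/25 × [1 + (50/14 − 1) × ICC]): 0.28 at ICC 0, 0.30 at 0.05 and 0.32 at 0.10. The chance of a difference above 0.25 SD is then 38%, 41% and 43%. A baseline difference d shifts a final-score comparison by ρd and a change-score comparison by −(1 − ρ)d. For d of one such SD:
- final scores, ρ = 0.5 to 0.7: from 0.5 × 0.28 = 0.14 to 0.7 × 0.32 = 0.22 SD towards the imbalance
- change scores, ρ = 0.5: 0.14 to 0.16 SD the other way; ρ = 0.7: 0.3 × 0.28 = 0.08 to 0.3 × 0.32 = 0.10 SD

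**Partial follow-up.** Suppose a fraction L of children is lost after the six-week visit, with equal correlation ρ among the three visits. Given baseline, the correlation of the two follow-up scores is p = ρ/(1 + ρ). The per-arm variance at six months is (1 − ρ²)/(25(1 − L)) for complete-case ANCOVA and (1 − ρ²)/25 × [p² + (1 − p²)/(1 − L)] for a repeated-measures model. At L = 20% the SEs of the difference are:
- ρ = 0.5: final-score t-test 0.316, ANCOVA 0.274, repeated measures 0.271
- ρ = 0.7: 0.316, 0.226, 0.222

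Over L = 10% to 30%, the repeated-measures step saves about 1% to 3% in SE. Nearly all the gain comes from baseline adjustment.

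**Clustering.** The size-weighted mean cluster is (10 × 3² + 4 × 5²)/50 = 3.8, so the design effect 1 + 2.8 × ICC is 1.14, 1.28 and 1.56 at ICC 0.05, 0.10 and 0.20. Tests that ignore school give intervals too narrow by 1 − 1/√1.14 = 6%, 1 − 1/√1.28 = 12% and 1 − 1/√1.56 = 20%.

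**The case against.** Three stronger readings are tempting, and the protocol does not support them.

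- A reader might infer that the baseline scores are ignored. Section 3.3.14 speaks twice of change, so a change-score test, which uses baseline, is open. What stands is that the choice is not stated and that change scores are still less efficient than adjustment.
- A reader might infer that the named tests cannot honour section 3.3.12. Separate comparisons at each visit would use the six-week data of a child lost later, which is arguably what that section promises. What stands is that those data add nothing to the six-month comparison, a small loss.
- A reader might infer that the reported intervals will simply be too wide. They are wider than those of an adjusted analysis that handles clustering in the same way. But the named tests make no allowance for school, and that pushes the reported intervals the other way.

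There are also general defences. Randomisation makes the unadjusted comparison unbiased on average, so this is a matter of efficiency and of chance imbalance in the one trial that is run. Schools are stratified and a local group will compare the arms for equivalence, but the stratification factors are all school-level. Eligibility requires scores beyond SDQ or DBC cut-offs (section 3.3.9), which tends to lower ρ; at 0.3 the gain over final scores is only 4%. The study is unpowered, its primary outcomes are utility and acceptability, and the raw data will allow the correlation to be computed later. All this limits the impact. It does not remove it, because the outcome estimates are meant to size the next trial. Covariates are often left to a statistical analysis plan, but here the protocol itself fixes the tests.

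**Conclusion.** The point holds as a matter of efficiency and clarity: the named tests have no baseline term, and the score to be compared is not fixed. Relative to a baseline-adjusted analysis with the same handling of school, 95% intervals are about 4% to 38% wider for final scores and 7% to 23% wider for change scores. Chance imbalance of a quarter of an SD or more is quite likely and would be left in (final scores) or over-corrected (change scores). The part that concerns partial follow-up is minor.

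The sizes rest on assumed correlations of 0.3 to 0.7, equal SDs over time, an even split of children and assumed ICCs up to 0.10 for the imbalance, none of which the protocol establishes. The change should be made, but no conclusion on the primary outcomes depends on it.

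**What to change.** For outcomes with a baseline, replace the two-sample tests in section 3.3.14 with a baseline-adjusted linear model that accounts for school. One suitable form is a mixed model over the six-week and final scores, with baseline score, arm, time and arm-by-time as fixed effects and random effects for school and child. Analyse children in their allocated arm and use all observed follow-up visits; this also gives effect to section 3.3.12. Keep simple comparisons for measures without a baseline, such as the Intervention Rating Profile.

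Alongside the raw SDs, report the baseline-follow-up correlation and the adjusted residual SD for the full trial's sample size.

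The cost is a change of wording and modest extra analysis; no new data are needed. With about 14 schools, the model calls for a small-sample correction.
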